## 12.6 Safety Oversight

The study Medical Monitor will review all adverse events and adverse device events that are reported during the study. SAEs will typically be reviewed within 24-hours of reporting. Other AEs will typically be reviewed approximately weekly.

A Data and Safety Monitoring Board (DSMB) will be informed of all cases of severe hypoglycemia and diabetic ketoacidosis irrespective of device relationship, all UADEs during the study and will review compiled safety data at periodic intervals. The DSMB also will be informed of any SADEs and ADEs not meeting criteria for a UADE if the Medical Monitor requests the DSMB review. The DSMB can request modifications to the study protocol or suspension or outright stoppage of the study if deemed necessary based on the totality of safety data available. Details regarding DSMB review will be documented in a separate DSMB Charter.

## 12.7 Stopping Criteria

### 12.7.1 Participant Discontinuation of Study Participation

In the case of a UADE, the Medical Monitor will determine if the use of the study device will be suspended while the problem is diagnosed. The use of the study device may continue if the Medical Monitor believes the event is explainable, unlikely to reoccur and that it is safe for the subject to continue using the device. Alternately, the Medical Monitor may request the study subject, or all study subjects, to stop using the study device or to only use in Manual Mode. Should all study subjects be required to stop using the study device or to only use in Manual Mode due an UADE, use of the study device or Automated Mode will not be restarted until approval is received from the IRB, DSMB and FDA.

Use of the study device by a participant will be discontinued if any of the following occur:

- The investigator believes it is unsafe for the participant to continue on the intervention. This could be due to the development of a new medical condition or worsening of an existing condition; or participant behavior contrary to the indications for use of the device that imposes on the participant's safety.
- The participant requests that the treatment be stopped
- Participant pregnancy
- Two distinct episodes of DKA as defined above
- Two distinct severe hypoglycemia events as defined above
- One episode of DKA and one severe hypoglycemia event as defined above

An additional requirement for continued study device use following a single DKA or severe hypoglycemia event will be that (1) the site investigator believes that the event is explainable, unlikely to recur, and that it is safe for the participant to continue to use the system and (2) the Medical Monitor concurs. If the Medical Monitor determines that the occurrence of the event indicates that it is not safe for the participant to continue to use the system, use will be discontinued, and the subject will be withdrawn from the study.

### 12.7.2 Criteria for Suspending or Stopping Overall Study

Stopping criteria for Phase 2 will be determined by an independent DSMB, who will assess the specific event rates for DKA and severe hypoglycemia from the study at specific timepoints relative to published rates from large, population-based datasets. Stopping rules may be modified for the Phase 3 extension.

In consideration of adverse events rates occurring in this proposed study, the rates will be assessed relative to published rates from Foster et. al. and Miller et. al. to determine whether severe hypoglycemia or diabetic ketoacidosis are within expected rates during this study Table 8: T1D Exchange Rates of Severe Hypoglycemia and Diabetic Ketoacidosis provides a summary of these published rates.

**Table 8: T1D Exchange Rates of Severe Hypoglycemia and Diabetic Ketoacidosis**

Adverse Event	Frequency of subjects to experience $\geq 1$ event extrapolated from T1DX registry 2016-2018, 2013-2014
Severe hypoglycemia (loss of consciousness or seizure)	4-5% < 18 years 7% $\geq 18$ years
Diabetic ketoacidosis (overnight hospitalization)	3-4% < 18 years 2-3% $\geq 18$ years

For unanticipated adverse device effects (UADEs), the DSMB will determine whether the study should proceed or not based upon risk of additional serious adverse events and the underlying root cause analysis of the UADE.

Study activities could be similarly suspended if the manufacturer of any component of the investigational study device requires stoppage of device use for safety reasons (e.g. product recall).

The affected study activities may resume if the underlying problem can be corrected by a protocol or system modification that will not invalidate the results obtained prior to suspension.

The study Medical Monitor will review all adverse events that are reported during the study, and the DSMB will review all cases of severe hypoglycemia, DKA and UADEs as well as compiled safety data at periodic intervals. The Medical Monitor and/or DSMB may recommend suspension of study activities or stoppage of the study to the Sponsor if deemed necessary based on the totality of safety data available.

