### **12.3.3 Hypoglycemic Events**

Hypoglycemia is only reportable as an adverse event when one of the following criteria is met:

- Severe Hypoglycemia: The event required assistance of another person due to altered consciousness, and required another person to actively administer carbohydrate, glucagon, or other resuscitative actions. This means that the participant was impaired cognitively to the point that he/she was unable to treat himself/herself, was unable to verbalize his/her needs, was incoherent, disoriented, and/or combative, or experienced seizure or loss of consciousness. These episodes may be associated with sufficient neuroglycopenia to induce seizure or loss of consciousness. If plasma glucose measurements are not available during such an event, neurological recovery attributable to the restoration of plasma glucose to normal is considered sufficient evidence that the event was induced by a low plasma glucose concentration.
- Hypoglycemia resulting in an SAE that may not otherwise meet the definition of Severe Hypoglycemia defined above.

When a hypoglycemic event meets the above reporting requirements, an Adverse Event Form should be completed. A severe hypoglycemia event should be considered a serious adverse event and follow the SAE reporting requirements.

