### **12.3.4 Hyperglycemic/Ketotic Events**

Hyperglycemia is only reportable as an adverse event when any of the following criteria is met:

- The event involved DKA, as defined by the Diabetes Control and Complications Trial (DCCT) and described below
- Evaluation or treatment was obtained at a health care provider facility for an acute event involving hyperglycemia or ketosis, or the participant contacted the site and received guidance on how to manage the hyperglycemia/ketosis
- Prolonged hyperglycemia: defined as meter BG  $\geq 300$  mg/dL and ketones  $> 1.0$  mmol/L
- Hyperglycemia resulting in an SAE that may not otherwise meet the above criteria

Hyperglycemic events are classified as DKA if all of the following are present:

- Symptoms such as polyuria, polydipsia, nausea, or vomiting;

- Serum ketones >1.5 mmol/L or large/moderate urine ketones;
- Either arterial blood pH <7.30 or venous pH <7.24 or serum bicarbonate <15; and
- Treatment provided in a health care facility

When a hyperglycemia/ketotic event meets the above reporting requirements, Adverse Event Form should be completed.

Events meeting DKA criteria should be considered a serious adverse event and follow the SAE reporting requirements. Hyperglycemia events not meeting criteria for DKA generally will not be considered as serious adverse events unless one of the SAE criteria above is met.

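### The comparison of trial severe hypoglycemia and DKA with the registry rates in Table 8 is not like-for-like and can err in either direction

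*Protocol*

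**What the plan says.** Protocol Section 12.7.2 states that "the rates will be assessed relative to published rates from" two registry reports "to determine whether severe hypoglycemia or diabetic ketoacidosis are within expected rates during this study". Table 8 summarizes those rates as the percentage of subjects with at least one event. Its rows are labelled "Severe hypoglycemia (loss of consciousness or seizure" (4-5% under 18 years, 7% from 18 years) and "Diabetic ketoacidosis (overnight hospitalization" (3-4% and 2-3%). No observation period is given.

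The trial's events are defined elsewhere. Section 12.3.3 defines severe hypoglycemia thus: "The event required assistance of another person due to altered consciousness, and required another person to actively administer carbohydrate, glucagon, or other resuscitative actions". It goes on to include a participant who "was incoherent, disoriented, and/or combative, or experienced seizure or loss of consciousness". Section 12.3.4 classifies DKA only if symptoms, ketones, a pH or bicarbonate criterion and "Treatment provided in a health care facility" are all present; no overnight stay is needed. The primary safety endpoints are incidence rates per person-month (Protocol 13.2.1.1, SAP 3.1). The cohorts are 6-13.9 and 14-70 years (Protocol Table 1).

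Protocol 13.3 and SAP 2.5 make study success depend on the Phase 2 rates of these two events being acceptable against published rates. They name no source, and Table 8 is the only tabulated set. SAP 5.4 plans no formal safety test. Section 12.8 leaves the final stopping rules to the DSMB Charter.

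**The concern.** With no test or margin, the safety conclusion rests on whether the observed rates look acceptable beside the benchmark, so the two sides should count the same thing in the same people over the same time. They differ in event definition, age grouping, unit and entry restrictions, and neither document adjusts for this. So few events are expected that reclassifying one or two could change the impression. The error could run either way: a false signal or a hidden excess. It bears on both the DSMB's reading and the success statement at the end of Phase 2.

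**Working it through.** **Step 1: the two sides compared.** The last column is the effect on a device whose true rates equal the registry's.

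| Feature | Table 8 | Trial | Effect taken alone |
|---|---|---|---|
| Severe hypoglycemia | Seizure or loss of consciousness | Those, plus other assisted episodes with altered consciousness (12.3.3) | Looks worse |
| DKA | Overnight stay | Any facility, but full clinical and biochemical criteria (12.3.4) | Unknown: broader on setting, stricter on biochemistry |
| Age groups | Under 18, 18 and over | 6-13.9, 14-70 | See step 3 |
| Measure | Percent of subjects, no period | Events per person-month | See step 2 |
| Entry | No exclusion shown | Severe hypoglycemia in the past 6 months excluded; DKA too, with exceptions (7.1) | Looks better |

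**Step 2: unit and period.** Table 8 is extrapolated from sources outside the documents, so its figures cannot be reproduced. Converting a percentage p over T months to a rate uses h(p)/T, with h(p) = -ln(1-p). T is an assumption, shown at 12 and 3 months:

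| Severe hypoglycemia, p | Per 100 person-months, T = 12 | T = 3 |
|---|---|---|
| 4% | 0.340 | 1.361 |
| 5% | 0.427 | 1.710 |
| 7% | 0.605 | 2.419 |

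The unstated period alone moves the benchmark fourfold. If T = 12, the matching 13-week percentages are 1-(1-p)^(13/52.18) = 1.0%, 1.3% and 1.8%. A raw 13-week percentage set against 4%, 5% or 7% would then look about four times better (for example 7/1.79 = 3.9). If T = 3, this distortion almost vanishes.

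The Protocol Introduction also cites an annual 11.8% from the same registry, for severe hypoglycemia with seizure or loss of consciousness. That is 11.8/7 = 1.7 times Table 8's figure for 18 and over.

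**Step 3: age split, if the comparison is made by cohort.** Let s be the share of 14-17.9-year-olds in the 14-70 cohort (assumed 10-40%). The expected rate relative to the 18-and-over benchmark is [s h(p under 18) + (1-s) h(p 18+)] / h(p 18+). For severe hypoglycemia with s = 20% and 5% under 18: (0.2 x 0.0513 + 0.8 x 0.0726)/0.0726 = 0.94. Over the Table 8 ranges:

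| s | Severe hypoglycemia | DKA |
|---|---|---|
| 10% | 0.96-0.97 | 1.00-1.10 |
| 20% | 0.91-0.94 | 1.00-1.20 |
| 40% | 0.83-0.88 | 1.00-1.41 |

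The split flatters the device for severe hypoglycemia and is neutral or unfavourable for DKA.

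**Step 4: severe hypoglycemia definition.** Let k be all trial-defined events divided by those with seizure or loss of consciousness. The documents give no value; 1 to 3 is assumed. In the older cohort, k must exceed 1/0.97 = 1.03 to 1/0.83 = 1.21 to outweigh step 3. As an illustration, take T = 12, 13 weeks, 100 subjects at 4.5% and 100 at 7%. The benchmark is 100 x (0.0460 + 0.0726) x 13/52.18 = 2.96 events. Seven is the smallest count with Poisson probability below 5% at that mean; it is not a rule in the documents.

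| k | Expected events | Chance of 7 or more |
|---|---|---|
| 1 | 2.96 | 3.1% |
| 1.5 | 4.43 | 16% |
| 2 | 5.91 | 38% |
| 3 | 8.87 | 78% |

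This isolates one mismatch at the end-of-Phase-2 exposure, which is the success comparison and not a scheduled DSMB review.

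**Step 5: the scheduled DSMB review.** Section 12.8 sets one pivotal review before the end of Phase 3, after at least 80 subjects reach about 24 days. The minimum exposure is 80 x 24/365.25 = 5.26 person-years. At 5% a year, 5.26 x 0.0513 = 0.27 severe hypoglycemia events are expected; at k = 3, 0.81. If Table 8 covered 3 months, the k = 1 figure would be 4 x 0.27 = 1.08. Exposure may be larger, since 80 is a minimum.

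**The case against.** The operative stopping rules sit in the DSMB Charter, which is not available and may align the definitions. The DSMB is told of every severe hypoglycemia and DKA case and weighs all the safety data (12.6, 12.7.2). The Medical Monitor adjudicates each one (12.9). With a handful of cases, an independent board can see which involved a seizure, and Table 8 shows its restriction openly. Nothing describes an automatic stop. Section 12.7.2 does not say that the comparison is by the 14-year cohorts, so the age point is conditional.

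All of this stands and limits the harm from the stopping comparison. It does not make the benchmark like-for-like: the protocol presents Table 8 as the comparator without qualification, and no case-by-case board review is described for the success comparison.

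A reader might go further and infer that a device matching the registry would look worse, or that wrongful stopping is likely. The documents do not support that. Only the severe hypoglycemia definition pushes clearly that way. The age split for that event, the entry exclusions and an uncorrected annual period push the other way, and the DKA definition has no derivable direction. The larger percentages in step 4 rest on an assumed multiplier and cut-off, at an exposure that no scheduled DSMB review shares.

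**Conclusion.** The mismatch is established from the documents' own wording: event definitions, age groups and units differ between the trial and Table 8, and nothing reconciles them. For severe hypoglycemia, the definition taken alone raises the trial count. For DKA, the definition effect has no known sign. The age effect applies only if the comparison is by cohort, and the fourfold unit effect only if Table 8 is annual and percentages are compared raw. The net size and sign cannot be derived; k, s and T are all assumptions. At the scheduled pivotal DSMB review, so few events are expected that the practical effect on stopping is probably small. The end-of-Phase-2 success comparison, with about 3 benchmark events under the step 4 assumptions, is where the mismatch matters more. It should be corrected because the conclusion depends on this comparison and the correction is cheap.

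**What to change.** Leave the endpoint definitions and the DSMB's review of every event as they are; no stopping threshold is proposed here. For the comparison with published rates, in the DSMB tables and at the end of Phase 2:

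- Add a matched tabulation of severe hypoglycemia with seizure or loss of consciousness, and of DKA with overnight hospitalization.
- Split it at under 18 and 18 years and over.
- State Table 8's observation period and put both sides in one unit, such as events per person-month with the conversion shown.
- Say why Table 8's adult figure is used and not the 11.8% in the Introduction.
- Have the Medical Monitor record two yes/no facts at adjudication: seizure or loss of consciousness, and overnight stay.

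The cost is two fields on events that are already adjudicated, plus wording in Section 12.7.2, the SAP and the DSMB tables. Age is collected at screening, and Section 12.5 already asks for discharge summaries when a subject is hospitalized with a serious event. The drawback is that the matched comparison rests on even fewer events, so it should stand beside the full counts and not replace them.

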### 12.8 Data Safety Monitoring Board (DSMB)

The DSMB will be established prior to the first enrollment and consist, at a minimum, of two physicians and one statistician independent from the Sponsor and study. The physicians will have relevant therapeutic and medical expertise.

The DSMB will determine the stopping criteria for the study and review Severe Hypoglycemia and DKA as well compiled safety data at periodic intervals to determine if the stopping rules apply. Stopping rules may be modified for the Phase 3 extension.

Compiled safety data may include listings of protocol deviations, device deficiencies, subject terminations, and/or subject withdrawals related to device or procedure safety. In addition, the DSMB members will be notified upon the occurrence of any UADEs to determine whether the study should proceed or not based upon risk and may request an ad hoc meeting to discuss. At minimum, the DSMB will conduct reviews after 16 subjects from the prepivotal study have completed a minimum of 10-days of the hybrid closed-loop phase (and prior to commencement of Pivotal Phase 2 for any subjects that did not participate in Prepivotal Phase 2), at the conclusion of the prepivotal study, after at least 80 pivotal subjects have completed study visit 7 (24 ± 3 days of HCL therapy), and after the end of Phase 3. Additional reviews may be conducted at any time based on the request of the DSMB, Sponsor or Medical Monitor. At the conclusion of each meeting, the DSMB will make a recommendation to the Sponsor concerning the continuation, modification, and/or termination, of the study and/or a statement regarding their overall assessment of device safety and continuation of the pivotal study. The final decision regarding the continuation, modification or termination of the study will reside with the Sponsor. Responsibilities, qualifications, membership and committee procedures, including the final stopping rules, will be outlined in the DSMB Charter.

## 12.9 Medical Monitor

An independent Medical Monitor will be responsible for individual and timely review of adverse events as defined below. The Medical Monitor will be a physician with relevant therapeutic and medical expertise that is not participating as an Investigator in the study and does not have a financial, scientific, or other conflict of interest with the clinical study.

Specific responsibilities of the Medical Monitor include:

- Review of all adverse events reported during the study
- Review all serious study procedure-related and/or investigational device-related adverse events to determine if the adverse event warrants consideration as a UADE and facilitate the reporting of UADEs if applicable
- Adjudicate the following(a) all SAEs; (b) any events of Diabetic Ketoacidosis or Severe Hypoglycemia; (c) all AEs reported by the site as related or possibly related to the investigational device; and/or (d) any additional events as requested by the Sponsor.
- The specified events will be adjudicated to determine:
  - event relatedness to the study procedures and/or the investigational device
  - event categorization and assess seriousness and severity
  - whether an adverse event is anticipated or unanticipated

The adjudication decision of the Medical Monitor will be used for the final classification of events, including relatedness to the study procedures and/or the

investigational device, for the determination of safety endpoints and for all regulatory reports, product labeling, and publications or presentations.

The Medical Monitor's roles and responsibilities are described in the Safety Management Plan (SMP).

## 13 STATISTICAL CONSIDERATIONS

### 13.1 Definition of Phase 2 and Phase 2 Participation

For the majority of subjects, Phase 2 of hybrid closed-loop data will include both data collected prior to a study pause and data collected after the recommencement. Unless otherwise specified, any data that may have been collected during a study pause (including but not limited to CGM readings from the Horizon system while in Manual Mode), will be excluded from analyses.

Continuous Phase 2 participation refers to the length of time on the Horizon system (either in Automated or Manual Modes) and is calculated as:

- Commencement of Phase 2 until a study pause (for subjects who started Phase 2 prior to a study pause)
- Recommencement until discontinuation from the Horizon system or end of Phase 2 (for subjects who started Phase 2 prior to a study pause)
- Commencement of Phase 2 until discontinuation from the Horizon system or end of Phase 2 (for subjects who started Phase 2 after a study pause)

If a subject has  $\geq 6$  weeks on the Horizon system during Phase 2 prior to a study pause and  $\geq 6$  weeks on the Horizon system during Phase 2 after the recommencement, the longer interval will be used for analysis of A1C. Specifically, the A1C associated with the longer interval, if available, will be used for the analysis of the A1C endpoints.

### 13.2 Objectives and Endpoints

#### 13.2.1 Primary Safety Objective

The primary safety objective of the study is to evaluate the safety of the Omnipod Horizon™ System in patients with type 1 diabetes.

##### 13.2.1.1 Primary Safety Endpoints

The primary safety objective will be evaluated by summarizing the following events during Phase 2, and separately during Phase 3:

- Incidence rate of severe hypoglycemia (events per person months)
- Incidence rate of diabetic ketoacidosis (DKA) (events per person months)

### 13.2.2 Primary Effectiveness Objective

The primary effectiveness objective of this study is to evaluate the effectiveness of the Omnipod Horizon™ System

#### 13.2.2.1 Primary Effectiveness Endpoints

There are two primary effectiveness endpoints.

- A1C after at least 6 weeks of continuous Phase 2 participation compared to baseline
- A1C at Visit 16, 19, 21, and 23 compared to baseline
- Percentage of time in range (70-180 mg/dL) during Phase 2 and separately during Phase 3 of the hybrid closed-loop phase as compared to Phase 1 (standard therapy)

#### A1C – Phase 2

A1C after at least 6 weeks of continuous Phase 2 participation will be compared to baseline A1C as measured by the core laboratory by calculating the change from baseline in A1C at the appropriate follow-up visit for each subject. Given the nature of this measure, continuous device use is essential for unbiased measurement of A1C. Therefore, the follow-up A1C used in the analysis of this endpoint will include only data from the subjects with at least 6 weeks of continuous Phase 2 participation, either prior to study pause or after recommencement, depending on the length of continuous participation and availability of the A1C measurements. The A1C collected at the latest follow-up visit during Phase 2 will be used, assuming it was collected after at least 6 weeks of subject's participation in Phase 2.

The change in A1C is calculated as A1C at follow-up minus baseline A1C (where negative change indicates decrease or improvement in A1C). The null hypothesis associated with this endpoint states that the mean change in A1C is greater than or equal to zero. Rejection of the null hypothesis indicates that the observed data support the alternative hypothesis that the mean change in A1C is less than zero.

The hypotheses associated with the first primary endpoint are defined as:

$$H_0: \mu \geq 0$$

$$H_1: \mu < 0$$

where  $\mu$  is the mean of the per subject differences in A1C from baseline to follow-up.

#### A1C – Phase 3

A1C at Visit 16 (~6 months total HCL participation) will be compared to baseline A1C as measured by the core laboratory by calculating the change from baseline in A1C at follow-up visit for each subject.

The change in A1C is calculated as A1C at follow-up minus baseline A1C. There are no hypotheses associated with this endpoint.

